7.2 POTENTIAL BENEFITS

There will be no direct benefit to participants in this study. However, the information that we get from the study may ultimately help the Food and Drug Administration decide how best to regulate tobacco products with the goal of improving public health.

8 DEFINITION OF ENDPOINTS

Screening: A variety of questionnaires and assessments will be used for the purpose of determining eligibility. This includes a Demographics Questionnaire, expired breath Carbon Monoxide reading, Physiological and Medical History Questionnaire, urinary pregnancy test, and a detailed Tobacco Use History Questionnaire.

Baseline: For participants who have been determined to be eligible, additional baseline questionnaires will be administered including a Stages of Change Questionnaire which assesses a participant's interest in quitting, smoking dependence questionnaires including Fagerstrom Test for Nicotine Dependence, Penn State Cigarette Dependence Index, and the Brief Wisconsin Inventory of Smoking Dependence Motives.

Daily Diaries: Daily diaries will assess the number of cigarettes used each day, as well as the number of IQOS Heat Sticks used. We will assess which product (cigarette or IQOS) was preferred and which was used first each day. Participants will be enrolled in these daily diaries at the baseline session and will continue to complete them each day until the Follow up session when they are

unenrolled. The primary outcome obtained using the daily diaries is the average number of cigarettes smoked during the baseline and sampling weeks.

Lab Session 2: Sampling: Participants will sample a traditional cigarette and the IQOS product. Participants will sample each product (four puffs at their own pace), and then wait 15 minutes before sampling the next product or beginning the preference assessment (i.e., 15-minute interproduct interval). During the interproduct interval, participants will complete questionnaires about the product they just sampled, each designed to assess the subjective effects and reinforcement value of the product they just sampled. After sampling the traditional cigarette, participants will complete three questionnaires. 1) The Cigarette Evaluation Scale, which assesses the sensory characteristics of the cigarette. Five subscales can be created from this assessment as previously described [6]: Satisfaction subscale, Psychological Reward subscale, Aversion subscale, Enjoyment of the Sensations in the Respiratory Tract subscale, and Craving subscale. 2) the Cigarette Purchase Task which assesses how many cigarettes participants estimate they would smoke at a variety of prices. As previously described [7], the following parameters can be calculated from this questionnaire: Intensity, or the number of cigarettes participants estimate they would smoke if cigarettes were free; Omax, or the maximum amount of money participants report they would spend in a single day; Pmax, or the price that produces Omax, Breakpoint, or the highest price at which participants report they would continue to smoke, and alpha, or the elasticity of demand for smoking. 3) the Perceived Health Risks scale, which assesses personal health risks associated with smoking. After sampling the IQOS product participants will complete four questionnaires.: 1) the Product Evaluation Scale, adapted from the Cigarette Evaluation Scale, which asks participants to rate the product on sensory characteristics (e.g., tasted good, immediately reduced craving for cigarettes). This questionnaire is analyzed in the same way as the Cigarette Evaluation Scale. 2) a modified Cigarette Purchase Task, in which participants estimate how many cigarettes they would smoke at a variety of prices if IQOS were also available (a test of whether the product reduces the reinforcement value of cigarettes), 3) a Product Purchase Task in which participants estimate how many Heat Sticks they would use across a series of prices if it were the only tobacco product available (a test of the reinforcement value of IQOS. Both the modified Cigarette Purchase Task and the Product Purchase Task are analyzed in the same way as the Cigarette Purchase Task. 4) a Perceived Health Risks scale, which assesses personal health risks associated with IQOS, and is the same scale used for traditional cigarettes.

Lab Session 2: Preference Assessment: After completing the sampling portion of this session, participants will complete the preference assessment. Preference Assessments have been used in a variety of contexts to determine reinforcement value. Across a series of trials, participants will have the option to choose either a traditional cigarette or IQOS. The primary outcome is the product most preferred.

Lab Session 3: Follow-up Questionnaires: After participants have taken home and sampled their assigned product for one week, they will return to the lab to complete a variety of follow-up questionnaires. This includes expired carbon monoxide (an objective marker of changes in smoke exposure compared to baseline), and the four questionnaires they completed about each product during the sampling session, this time completed about the product they took home with them for the week (Product Evaluation Scale, modified Cigarette Purchase Task, Product Purchase Task, Perceived Health Risks).

9 STATISTICAL CONSIDERATIONS AND DETERMINATION OF SAMPLE SIZE

9.1 DETERMINATION OF SAMPLE SIZE

The primary purpose of the proposal is to collect pilot data to lead to a larger grant submission. No formal power analysis has been conducted, and the sample size was chosen based on feasibility. A prior ITC pilot study conducted by [name] recruited 30 participants using a similar design with more restrictive inclusion criteria, and we anticipate being able to recruit 10 participants in the time proposed.

9.2 DATA ANALYSIS

For each of the questionnaires completed during Visit 2 sampling, the IQOS device will be compared to traditional cigarettes using paired-sample t-tests. A chi-square test will determine whether there are differences in the percentage of participants who preferred the IQOS and the percentage who preferred traditional cigarettes during the preference assessment. For the at-home sampling phase, a within-subjects t-test will determine whether there are differences in the average number of cigarettes smoked during baseline and the sampling week.

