5 PROCEDURES

Design Overview: After completing a screening/baseline session, current smokers will complete a one-week baseline period. Participants will then attend a lab-reinforcement session where they will sample the IQOS product and a traditional cigarette. We will provide transportation via a taxi cab company (Yellow Cab) for participants who are eligible, but do not have reliable transportation to in-person visits. We will pay the cab company directly, the participant will not need to contribute. Participants will complete questionnaires that assess subjective effects and reinforcement value of these products. Participants will complete a preference assessment designed to assess the relative reinforcement value of these products (see below for details). At the end of the session participants will receive an IQOS to take home with them for a one-week sampling period. Across the at-home baseline and sampling weeks, participants will complete electronic daily diaries cataloging their tobacco use.

The HTP device used will be the IQOS device. Participants will receive a rechargeable IQOS device and charger. Each Heat Stick is considered to be similar in nicotine delivery to a cigarette. Thus, to ensure participants have a full supply for the one-week period, we will provide 7 packs of Heat Sticks, one for each day. Again, this supply ensures participants could exclusively use IQOS across the entire sampling period, although we expect that the majority of participants will not do so. Heat sticks will be available in both traditional tobacco and menthol flavors (participant's choice).

Experimental Design:

Study design for both studies follows our prior and ongoing studies, and all procedures including diaries, are well established. Prior to attending the in-person screening session, participants will complete an online screening questionnaire to determine preliminary eligibility and may be consented remotely (see below for details). If consent is not completed remotely, it will be completed in person at the Screening/Baseline Session prior to collection of any data.

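### Does Section 9.2's single IQOS-versus-cigarette t-test rule leave the modified Cigarette Purchase Task, and purchase-task scores at zero demand, without a usable analysis?

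*Combined protocol and SAP*

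**What the plan says.** Section 9.2 gives one rule for the Visit 2 sampling questionnaires: "For each of the questionnaires completed during Visit 2 sampling, the IQOS device will be compared to traditional cigarettes using paired-sample t-tests".

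Section 8 (Lab Session 2: Sampling) describes an uneven set. On the cigarette side: "After sampling the traditional cigarette, participants will complete three questionnaires". On the IQOS side: "After sampling the IQOS product participants will complete four questionnaires". The extra one is a purchase task. The schedule in Section 6 confirms three purchase tasks at Visit 2: UB, Cig + IQOS, and IQOS.

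The Product Purchase Task asks "how many Heat Sticks they would use across a series of prices if it were the only tobacco product available". The modified Cigarette Purchase Task asks for cigarette consumption with IQOS on offer as well, and Section 8 describes it as "a test of whether the product reduces the reinforcement value of cigarettes".

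Five indices come from each task: Intensity, Omax, Pmax, Breakpoint and alpha. Section 8 takes their calculation from reference 7, a study of reduced-nicotine cigarettes and price sensitivity, and summarises the last three as "Pmax, or the price that produces Omax, Breakpoint, or the highest price at which participants report they would continue to smoke, and alpha" (the elasticity of demand). It adds: "Both the modified Cigarette Purchase Task and the Product Purchase Task are analyzed in the same way as the Cigarette Purchase Task".

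**The concern.** Two things look missing.

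First, the modified task measures cigarettes, not IQOS, so a rule that compares IQOS with cigarettes does not literally apply to it. Sorting out the pairing matters because a fall means different things in the two possible contrasts. If Heat Sticks alone score below cigarettes alone, IQOS is the weaker reinforcer. If cigarettes with IQOS on offer score below cigarettes alone, IQOS is displacing cigarettes. Reporting one as the other would reverse the message on a stated objective, in a pilot meant to support a grant application.

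Second, if a participant would buy nothing at any positive price, Omax is 0, every price attains it, and Pmax is not unique. Alpha has no paid consumption to fit. Dropping such pairs would favour IQOS in the IQOS-only contrast. In the modified contrast it would remove the people who switch fully, who show most strongly the effect that the task is meant to detect.

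**Working it through.** The plan gives no figure to reproduce: Section 9.1 reports no power calculation, and n = 10 rests on feasibility. The first part is a reading of the text. The second is arithmetic on assumed inputs.

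**1. Which task pairs with which**

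| Task | Counts | Available products |
|---|---|---|
| Cigarette Purchase Task | cigarettes | cigarettes |
| Product Purchase Task | Heat Sticks | IQOS only |
| Modified Cigarette Purchase Task | cigarettes | cigarettes and IQOS |

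Three tasks allow 3 pairwise contrasts, or 3 × 5 = 15 index comparisons.

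- Product versus Cigarette Purchase Task is the only pair that sets an IQOS score against a score for cigarettes alone. It is the 9.2 comparison.
- The modified task asks whether cigarette value is reduced. A reduction needs a reference level, and the only Visit 2 measure of cigarette demand without IQOS is the Cigarette Purchase Task. That fixes the second contrast.
- Modified versus Product Purchase Task answers no question that the plan poses.

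So there are 2 contrasts × 5 indices = 10 tests. Take an assumed Intensity of 20 cigarettes alone, 20 Heat Sticks alone and 10 cigarettes with IQOS on offer. The contrasts are 20 − 20 = 0 and 10 − 20 = −10 (−50%). They differ because they answer different questions. The tasks carry different names and count different things, so they are hard to confuse. Section 8's sentence on analysing the tasks alike follows the list of indices and concerns scoring, so it does not disturb this pairing.

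**2. Zero demand: which indices are affected**

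Omax is the largest value of price × quantity. If quantity is 0 at every positive price, Omax = 0. Intensity and Omax still have values. Pmax and alpha do not. Breakpoint is 0 for someone who takes only free product, and has no value for someone who takes none even when free.

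**3. Zero demand: size in the IQOS-only contrast**

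Assumptions: bivariate normal scores, correlation 0.5, and the lowest k of 10 second-task values dropped. The mean shift towards IQOS in simulation is 0.087, 0.160, 0.229 and 0.299 SD for k = 1 to 4. For k = 1 to 3 it is 0.05 to 0.14 at correlation 0.7 and 0.12 to 0.32 at correlation 0.3.

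Expected shift = Σ P(k) × shift(k), with k binomial(10, p). At p = 0.05: 0.315 × 0.087 + 0.075 × 0.160 + 0.010 × 0.229 + … ≈ 0.042 SD. At p = 0.02 it is 0.017, and at p = 0.10 it is 0.082.

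Standard error = √[2(1 − 0.5)]/√10 = 0.316 SD. The expected shift is therefore 5% to 26% of one standard error (0.017/0.316 to 0.082/0.316).

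Section 4.1 makes low rates plausible. Participants smoke at least five cigarettes daily and rate their interest in non-cigarette tobacco above 5 out of 10, and in this task IQOS is the only product on offer.

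**4. Zero demand: size in the modified contrast**

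Section 5 says of the take-home supply that "participants could exclusively use IQOS across the entire sampling period, although we expect that the majority of participants will not do so". Home use is not the task, but it suggests 0 to 4 full switchers of 10 as a rough range. Under the same model a true fall of 0.5 SD becomes 0.41, 0.34, 0.27 or 0.20 SD after losing 1 to 4 pairs (0.5 minus the shifts above). Power goes from 29% to about 21%, 15%, 10–11% and 7–8%. These figures give each zero-demand participant a hidden Pmax or alpha, which step 2 shows does not exist, so they describe the model more than the trial. Omax keeps those participants: if switching is all-or-none, mean Omax falls by 10% for each switcher in 10.

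**The case for a change.** The best case for acting is that 9.2 is the analysis section and, read literally, would label the modified task's result as IQOS against cigarettes. Naming two contrasts costs a few sentences, and the grant application would inherit any mislabelling. Under zero demand the scoring choice can matter. In a constructed set of ten with two undefined IQOS Pmax values, the mean difference is 0.0 if the pairs are dropped, −0.3 if they are set to 0, and +1.3 if they are set to the top price. Nor is one non-buyer far-fetched: at assumed rates of 5% or 10%, the chance of at least one in ten is 1 − 0.95¹⁰ = 40% or 1 − 0.90¹⁰ = 65%.

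What stands is that 9.2 does not name the modified task's comparator and that the text has no zero-demand rule. Whether reference 7 has one cannot be confirmed here. By its title that study would not name an IQOS contrast, but Section 8's stated aim does that work.

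The rest does not carry. The literal reading is impossible to execute, because the modified task contains no IQOS score, so it cannot mislead an analyst for long. Leaving a cited scoring method unrepeated is not shown to be a defect. The constructed Pmax differences are not significant (p = 1.0, 0.28 and 0.18), and the example shows sensitivity to arbitrary scores, not an error in the plan. The obvious remedy, calculating Pmax and alpha only among buyers in both tasks, is the same exclusion that is said to cause the bias. It would disclose the bias without removing it. Fixing a raw scale for the indices has no support in the documents and could conflict with the cited method.

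**Conclusion.** No change is needed. The missing comparator is a gap that Section 8 fills: its aim for the modified task and the set of Visit 2 measures lead to two contrasts, each against the ordinary Cigarette Purchase Task. A sentence saying so would be harmless but would alter no result.

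The zero-demand point touches Pmax and alpha, and Breakpoint for someone who would take nothing even free. It depends on a scoring source that could not be consulted, and prescribing exclusion would gain nothing. In the IQOS-only contrast the expected effect is 0.02 to 0.08 SD against a standard error of 0.32 SD. In the modified contrast it could be larger, but Omax still registers full switchers.

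All rates, SDs and correlations here are assumed. The weight is small in any case: ten participants chosen for feasibility, no prior hypothesis about either product (Section 2.1), and no effect on diary cigarette counts or product preference, the two outcomes that Section 8 calls primary. The judgement would be different if the purchase-task indices were primary or were to support a confirmatory claim.

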1) Screening/ Baseline session and Baseline Smoking Phase: Participants will attend an in-person screening session in which they complete a battery of assessments to determine eligibility. Eligible participants will then complete a series of baseline questionnaires. At the end of the baseline session, participants will be instructed to smoke as normal for a one-week baseline period. Participants will enroll in daily electronic diaries documenting their tobacco use and will complete the first diary in the lab with help of study staff. Participants will provide a urine sample for baseline assessment of cotinine (the primary metabolite of nicotine).

2) Laboratory Reinforcement Session: Participants will attend a lab session in which they sample the IQOS product and a traditional cigarette and complete questionnaires about each product they sample (see below).

Sampling and Product Questionnaires:

Participants will sample the IQOS product (n=10) and a traditional cigarette (traditional cigarette first). For each product, participants will take four puffs at their own pace, and then complete a series of questionnaires assessing the subjective effects and reinforcement value of the product (see below). There will be a 15-minute inter-product interval. When participants finish the questionnaires about each product, they will wait for the remainder of the 15 minutes to elapse before trying the next product. Participants can play on their phones or read a magazine during this time. Study staff will be able to see and hear the participant from the control room during this time and will guide the participant through the sampling session by giving directions as to when to try each product and when to start/stop questionnaires.

Preference Assessment:

At the end of the 15-minute period for the last product, participants will begin a preference assessment. For this preference assessment, participants will complete 10 trials with a 4-minute inter-trial interval. For each trial, a member of study staff will ask the participant to choose between the IQOS and a traditional cigarette. Participants will indicate which product they choose and then be allowed to take two puffs of the product at their own pace. For each trial, participants may also choose not to take any puffs.

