6 STUDY

Timepoints	Screening / Baseline	Lab Session 2 Reinforcement Session	Lab Session 3 Follow up Session
Assessments			
Informed Consent	X		
Demographics	X		
Carbon Monoxide	X	X	X
Pregnancy Test	X		
Physiological and Medical History	X		
Tobacco Use History	X		
Adverse Event Monitoring		X	X
Timeline Followback	X	X	X
Cotinine	X		X
Stages of Change	X		
Fagerstrom Test for Nicotine Dependence	X		X
Penn State Cigarette Dependence Index	X		X
Penn State Dependence –Assigned Product			X
Brief Wisconsin Inventory of Smoking Dependence Motives	X		X
Electronic Daily Diaries	Enroll→	→	→Unenroll
*Cigarette Evaluation Scale		X	
*Purchase Task (UB)		X	
*Perceived Health Risks (UB)		X	
*Product Evaluation Scale (IQOS)		X	
*Purchase Task (Cig + IQOS)		X	X
*Purchase Task (IQOS)		X	X
*Perceived Health Risks (IQOS)		X	X
Preference Task		X	X

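### Section 9.2 tests preference with an unspecified chi-square on at most 10 people and has no rule for participants whose choice counts are equal

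*Combined protocol and SAP*

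**What the plan says.** Section 5 (Procedures, Preference Assessment) says that "participants will complete 10 trials with a 4-minute inter-trial interval". On each trial the choice is between IQOS and a traditional cigarette, and there is a third option: "For each trial, participants may also choose not to take any puffs".

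Section 8 (Lab Session 2: Preference Assessment) reduces these choices to one category per person: "The primary outcome is the product most preferred". Section 9.2 then gives the test: "A chi-square test will determine whether there are differences in the percentage of participants who preferred the IQOS and the percentage who preferred" traditional cigarettes.

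The plan does not say how ten choices become one preference, what happens when the two counts are equal, which form of chi-square is meant, or what significance level applies. The Abstract and Section 9.1 put the sample at 10. On its basis, Section 9.1 says: "No formal power analysis has been conducted, and the sample size was chosen based on feasibility".

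**The concern.** An even number of trials allows a 5-5 result, and the opt-out also allows 4-4, 3-3 and so on down to 0-0. A participant with equal counts has no defined value on the outcome that Section 8 calls primary for this assessment. The tie rule would then be settled after the choices are known.

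The test form is equally open. Section 9.2 speaks of two percentages. An analyst could test one proportion against 50:50, or could set the percentages against each other in a 2x2 table as if they came from different people. With 10 people, these readings can give different answers from the same data.

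The choice counts themselves would also go unused. Section 5 describes the purpose thus: "Participants will complete a preference assessment designed to assess the relative reinforcement value of these products". Section 9.1 says: "The primary purpose of the proposal is to collect pilot data to lead to a larger grant submission". Yet no mean or SD of the choices is planned.

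**Working it through.** The plan gives no power, alpha or critical value for this test, so there is no figure to reproduce.

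**Inputs.** From the documents: 10 participants, 10 trials each, and a decline option on every trial. Assumed: two-sided alpha of 0.05 (Section 2.1 states no directional hypothesis), and preferred meaning the product chosen on more trials.

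**One-sample reading.** With a preferring IQOS, b preferring the cigarette and n = a + b untied, the chi-square is (a - b)²/n on 1 df. The exact test doubles the Binomial(n, 0.5) tail.

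- 7-1: (7 - 1)²/8 = 4.50, p = 0.034; exact p = 2 × (8 + 1)/256 = 0.070.
- 5-0: 5²/5 = 5.00, p = 0.025; exact p = 2 × 1/32 = 0.0625.

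**Tie rule, 7 IQOS / 1 cigarette / 2 tied.** Dropping the ties gives 0.034, as above. Splitting them gives 8-2: (8 - 2)²/10 = 3.60, p = 0.058.

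**2x2 reading.** At 8/10 against 2/10, chi-square = 20 × (8×8 - 2×2)²/(10×10×10×10) = 7.20, p = 0.007. With the Yates correction it is 20 × (60 - 10)²/10,000 = 5.00, p = 0.025. The one-sample statistic for the same data is 3.60 (p = 0.058), and the exact p is 0.109. The 2x2 statistic is twice as large because it treats two complementary percentages from the same 10 people as independent.

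**True type I error by number of untied people** (smallest rejected split in brackets; the last column is uncorrected, with tied people kept in the denominator of 10):

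| Untied | One-sample chi-square | Exact binomial | 2x2, out of 10 |
|---|---|---|---|
| 10 | 0.0215 (9-1) | 0.0215 (9-1) | 0.1094 (8-2) |
| 9 | 0.0391 (8-1) | 0.0391 (8-1) | 0.1797 (7-2) |
| 8 | 0.0703 (7-1) | 0.0078 (8-0) | 0.0703 (7-1) |
| 7 | 0.0156 (7-0) | 0.0156 (7-0) | 0.1250 (6-1) |
| 6 | 0.0313 (6-0) | 0.0313 (6-0) | 0.0313 (6-0) |
| 5 | 0.0625 (5-0) | 0 (none) | 0.0625 (5-0) |

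**Averaging over ties, one worked case.** Suppose that each person's chance of choosing IQOS is spread uniformly over 0 to 1 and nobody opts out. All 11 counts from 0 to 10 are then equally likely, so a person ties with probability 1/11. The probabilities of 10, 9, 8, 7 and 6 untied people are 0.3855, 0.3855, 0.1735, 0.0463 and 0.0081. Weighting the columns (smaller n is negligible):

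- 2x2: 0.0422 + 0.0693 + 0.0122 + 0.0058 + 0.0003 = 0.130.
- One-sample chi-square: 0.0083 + 0.0151 + 0.0122 + 0.0007 + 0.0003 = 0.037.
- Exact binomial: 0.0083 + 0.0151 + 0.0014 + 0.0007 + 0.0003 = 0.026.

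The uncorrected 2x2 form therefore runs from 10.9% without ties to about 13% with them. With Yates it is also 10.9% without ties, since 8-2 is still rejected. In the worked case it falls to 0.0422 + 0.0151 + 0.0122 + 0.0007 + 0.0003 = 0.0705, about 7%.

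**How often ties matter.** The documents give no opt-out rate or preference distribution, so this part is illustrative. Seven scenarios with a true preference were simulated at 10% opt-outs, with 20,000 runs each. At least one of the 10 participants tied in about 30% to 55% of trials. Dropping rather than splitting ties changed the 5% decision in about 2% to 4%.

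**The case against.** **The one-sample chi-square is adequate on average.** This stands. Over simulated null cases with 0%, 10% and 30% opt-outs it rejected in 2.7% to 4.3% of trials, and with 10 untied people it rejects exactly where the exact test does. A reader might infer that the planned test is inflated in general. That does not follow on the one-sample reading, where sizes above 5% occur only at particular numbers of untied people, such as 8 or 5. The 2x2 form is inflated, but Section 9.2 merely permits it and does not call for it.

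**A single tie need not overturn a clear result.** A reader might point to 8 IQOS / 1 cigarette / 1 tied, where p moves from 0.020 (tie dropped) to 0.058 (tie counted as not preferring IQOS). That rule merges ties with cigarette preference, and the text does not suggest it. Rules that treat the products alike agree here: 0.020 dropped and 0.027 split. Decision changes of 7% to 15% arise only under the asymmetric rule. The 7/1/2 case shows that symmetric rules can also disagree, but less often.

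**Graded reinforcement is measured elsewhere.** This stands too. Section 8 derives several demand measures from the purchase tasks, and Section 9.2 applies paired t-tests to the Session 2 questionnaires. The reinforcement objective does not rest on the preference category alone.

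**A test on choice counts is not clearly better.** Against the chi-square at 10% opt-outs, a sign-flip test on per-person differences had 47% against 35% power under one assumed spread. It had 44% against 61% when most people mildly prefer IQOS and a few almost always choose the cigarette. The documents do not support calling it the more powerful analysis.

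**The session is not really in doubt.** Sections 5 and 8 both place the assessment in the second session. The remaining conflict is in the schedule.

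**Conclusion.** The point holds in limited form. The outcome is undefined for a participant with equal counts, and the test is not identified. On the one-sample reading the practical effect is confined to a few splits, chiefly 7-1 and 5-0, and to about 2% to 4% of simulated trials for the choice between dropping and splitting ties. On the 2x2 reading the effect is larger: 8-2 is declared significant, and the uncorrected type I error is about 11% to 13% with 10 kept as the denominator.

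The p-values and the sizes by number of untied people are exact, given a two-sided 5% level and a majority-of-choices definition. The tie frequencies, averaged error rates and power figures rest on assumed preference spreads and opt-out rates.

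The consequence is minor. This is a feasibility pilot with no power claim and no stated direction. The change is still worth making, because it is cheap and removes a choice that could otherwise be made after seeing the data.

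**What to change.** In Section 9.2, before the choice data are analysed:

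- Define preferred as the product chosen on more of the 10 Session 2 trials, and equal counts (including 0-0) as tied.
- Report the numbers preferring IQOS, preferring the cigarette, and tied.
- Replace the chi-square with a two-sided exact binomial test on untied participants. Give an exact 95% confidence interval for the proportion preferring IQOS. For 8 of 10 that interval is 44% to 97%, which shows how little 10 people can settle.
- Report descriptively the mean and SD of each person's IQOS minus cigarette choices, and the number of declined trials, as pilot data for the later grant. Keep the person as the unit; do not pool the 100 choices as independent. A sign-flip test on these differences is optional and secondary.

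Separately, reconcile the Section 6 grid, which marks the "Preference Task" at Session 3 as well as Session 2, with Section 8, which omits it from the Session 3 assessments.

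The cost is a few sentences and no new procedure, since participants already state a choice on every trial. Against the one-sample chi-square, the exact test loses about 2 to 4 points of power under assumed 10% opt-outs (for example 35.3% to 31.8%). With no opt-outs the loss is up to 7 points (40.1% to 33.1%).
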